6.6.4. Missing End of Treatment Date

For patients without a full end of treatment date (i.e., missing day, month, or year), the last study drug dispensation date will be used as the end of treatment date for purposes of analysis.

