**Table 4: Schedule of Assessments**

	Screening Period		Treatment Period											
	Screen A a	Screen B b	Day 1 c	Wk 1 (Phone)	Wk 1	Wk 2 (Phone)	Wk 2	Wk 3 (Phone)	Wk 4	Wk 4 (Phone)	Wk 5 (Phone)	Wk 6	Wk 7 (Phone)	Week 8
	Up to Day -90	Up to Day -30	Day 1	Day 3 ±2 Days	Day 7 ±3 Days	Day 10 ±2 Days	Day 14 ±3 Days	Day 21 ±2 Days	Day 28 ±3 Days	Day 31 ±2 Days	Day 38 ±2 Days	Day 42 ±3 Days	Day 45 ±2 Days	Day 56 ±3 Days
Informed Consent/Assent	X													
Inclusion/Exclusion														
	X		X d											
Demographics & Baseline Disease Characteristics	X													
Prior and Concomitant Medications	X	X	X	X	X	X	X	X	X	X	X	X	X	X
Medical History	X													
Height e	X	X	X		X		X		X			X		X
Weight in Clinic	X		X		X		X		X			X		X
Weight at Home			-----X-----											
Dispense Weight & Study Drug Diary			X				X		X		X		X	X
Collect/Review Weight & Study Drug Diary				X	X	X	X	X	X	X	X	X	X	X
ECG	X													
Echocardiogram f	X													
Vital Sign Measurements	X	X e	X		X		X		X			X		X
Comprehensive Physical Exam	X		X											
Targeted Physical Exam					X		X		X			X		X
Pregnancy Test for WOCBP h	X	X	X						X					X
Study Drug Administration			-----X-----											

Dispense Study Drug			X				X		X			X		X
Collect Study Drug							X		X			X		X
Telephone Contact				X		X		X		X	X		X	
Adverse Event Collection			X i	X	X	X	X	X	X	X	X	X	X	X
Kidney Ultrasound j	X													
Clinical Chemistry (incl. eGFR) k	X	X	X		X		X		X			X		X
BNP and NT-proBNP	X		X		X		X		X			X		X
Hemoglobin A1c	X													
Hematology	X		X				X		X			X		X
Coagulation			X				X		X			X		X
Basic Lipid Panel			X											
Urinalysis and Microscopy	X		X				X		X			X		X
Urine Collection for ACR l		X							X					X
Virus Serology	X													
PK Samples n														
SARS-CoV-2 Antibody Test			X											
Ambulatory Blood Pressure Monitoring o	X p													
Tanner Staging q			X											

	Treatment Period								
	Wk 12	Wk 24	Wk 36	Wk 48	Wk 52 (B)	Wk 64	Wk 76	Wk 88	Wk 100 or End of Treatment
	Day 84 ±3 Days	Day 168 ±3 Days	Day 252 ±3 Days	Day 336 ±3 Days	Day 364 ±3 Days	Day 448 ±5 Days	Day 532 ±5 Days	Day 616 ±5 Days	Day 700 -5 Days (+0 Days)
Informed Consent/Assent									
Inclusion/Exclusion									
Demographics & Baseline Disease Characteristics									
Prior and Concomitant Medications	X	X	X	X	X	X	X	X	X

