**9.10.14. Study Drug Dispensation and Collection**

Study drug will be dispensed to the patient and collected from the patient as indicated in Table 4. The patient will be dispensed the appropriate number of treatment kits at each timepoint: Day 1, Week 2, Week 4, Week 6, Week 8, Week 12, Week 24, Week 36, Week 48, Week 52 (B), Week 64, Week 76, and Week 88. If the patient is provided more than one kit, only one treatment kit should be opened at a time. Dispensed treatment kits from each visit (including unscheduled visits) should be returned to the site for collection as indicated in Table 4 or at the subsequent visit.

If the appropriate number of treatment kits (e.g., a 3-month supply) cannot be dispensed as outlined in Table 4, a partial supply may be provided to the patient. The remainder may be provided separately to the patient. Every effort should be made to avoid interruptions in dosing.

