### 10.2. Study Drug Packaging and Labeling

The study drug will be supplied as either individual bottles (5, 10, 20 mg dose) or in tamper-evident kits containing two high-density polyethylene (HDPE) bottles (30 mg dose as 2 x 15 mg capsules). Each bottle will utilize foil induction-seal liners and a child-resistant closure. Each bottle of study drug will contain 30 capsules of 5 mg, 10 mg, 15 mg, or 20 mg strength bardoxolone methyl or the matching placebo capsules. Each bottle will also contain desiccant insert(s) that must not be ingested. Labeling on each kit bottle will contain at minimum the following information:

- Medication ID number;
- Protocol 402-C-1808;
- Caution Statement: New Drug – Limited by Federal Law to Investigational Use. Keep out of reach of children;
- Control or lot number;
- Store at 15° – 25°C (59° – 77°F);
- Reata Pharmaceuticals, Inc., Irving, TX.

When applicable, a double-panel label will be presented on the treatment kit carton containing this and other information. Additionally, labeling, in the relevant local languages for study drug use and distribution in the EU shall adhere to current Eudralex, Volume 4 Annex 13 guidance and requirements.

In the event the investigational product is not packaged as intended or may not adhere to Current Good Manufacturing Practices (CGMP), a complaint should be filed with the Sponsor, ideally through the site's CRA. Guidance on filing study drug complaints is available in the Study Reference Manual, and attention should be given to ensure the patient number is not submitted within the complaint documentation.

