Protocol specified 2 off-treatment chemistry values collected within the Week 52 (prior to protocol version 6), Week 104, Week 108 and Week 112 analysis window at A and B visits. At Week 52, Week 104, Week 108, and Week 112 visits, the 2 off-treatment measurements that are in the analysis window and closest to the target day specified in Table 4 are averaged for the purpose of data summary and analysis. All values included in the Week 103, 104, 108, and 112 analysis windows must also be assessed after last dose.

Records from visits not closest to the target study day, and therefore not used in analyses, are presented in by-patient data listings.

Table 4. ANALYSIS VISIT WINDOWS

Analysis Visit	Label	Target		Analysis Window
		Study Day ^a	Days After Last Dose	
1	Week 1	7	-	$2 \leq \text{study day} \leq 10$
2	Week 2	14	-	$11 \leq \text{study day} \leq 21$
4	Week 4	28	-	$22 \leq \text{study day} \leq 35$
6	Week 6	42	-	$36 \leq \text{study day} \leq 49$
8	Week 8	56	-	$50 \leq \text{study day} \leq 70$
12	Week 12	84	-	$71 \leq \text{study day} \leq 126$
24	Week 24	168	-	$127 \leq \text{study day} \leq 210$
36	Week 36	252	-	$211 \leq \text{study day} \leq 294$
48	Week 48	336	-	$295 \leq \text{study day} \leq 350$
52	Week 52	364	-	$351 \leq \text{study day} \leq 406$
64	Week 64	448	-	$407 \leq \text{study day} \leq 490$
76	Week 76	532	-	$491 \leq \text{study day} \leq 574$
88	Week 88	616	-	$575 \leq \text{study day} \leq 658$
100	Week 100 ^b	700	-	$659 \leq \text{study day} \leq 720$
103	Week 103 ^c	721	21	$721 \leq \text{study day} \leq 727^{\text{d}}$ or $21 \leq \text{after last dose} \leq 27^{\text{e}}$
104	Week 104 ^c	728	28	$728 \leq \text{study day} \leq 755^{\text{d}}$ or $28 \leq \text{after last dose} < 55^{\text{e}}$
108	Week 108 ^c	756	56	$756 \leq \text{study day} \leq 783^{\text{d}}$ or $56 \leq \text{after last dose} \leq 83^{\text{e}}$
112	Week 112 ^c	784	84	$784 \leq \text{study day} \leq 806^{\text{d}}$ or $84 \leq \text{after last dose} < 106^{\text{e}}$

^a Study Day is relative to the date of first dose (Section 6.5.1).

^b Week 100 is the end of the dosing interval and should coincide with the last dose.

^c Including off-treatment values only.

^d Analysis windows are based on study day for patients who discontinued treatment early. Analysis windows are based on days after last dose for patients who complete treatment. Last dose for analysis is the Week 100 dose.

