9.1. Adverse Event Preferred Term and Body/Organ System Summary Tables

Treatment-emergent adverse events are summarized by treatment as defined by the safety analysis set. In addition to being summarized by treatment year, AEs are also summarized overall.

Treatment-emergent adverse events are events that either:

- Have a complete date of onset on or after the date of first dose and not more than 30 days after the date of the last dose of study drug, or
- Have no recorded date of onset with a stop date after the first dose of study drug, or
- Have no recorded date of onset and stop date.

General considerations for TEAE summaries are:

- Multiple events by PT and SOC are counted once only per patient for summaries of TEAE incidence.
- For summaries of TEAE incidence by severity, only the most severe event is counted per patient.
- For summaries of TEAE incidence by relationship, only the most strongly related event is counted per patient.
- A TEAE with a missing resolution date or incomplete date that is not identified as continuing is assumed to be continuing.
- For summaries of the number of TEAEs, all TEAEs are counted.

Off-treatment AEs (OTAEs) are events with a start date more than 30 days after last dose and not considered treatment emergent. Off-treatment AEs will be summarized separately.

Adverse Events are coded using MedDRA. In MedDRA, each verbatim term is mapped to a preferred term and high-level term (HLT), which is then mapped to a SOC.

The investigator grades the severity of the AEs as mild, moderate, or severe as defined in the study protocol. The investigator grades association or relatedness to the study medication according to criteria specified in Section 11.4 of the protocol.

As defined in the protocol, an SAE is an adverse event (occurring at any dose and regardless of causality) that:

- Results in death;
- Is life-threatening;
- Requires inpatient hospitalization or prolongation of existing hospitalization;
- Results in persistent or significant incapacity or substantial disruption of the ability to conduct normal life functions;
- Is a congenital anomaly or birth defect in an offspring of a patient taking study drug;
- Is an important medical event.

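### An incomplete end-of-treatment date is set to the last dispensation date, which can be up to about 12 weeks before the true last dose and can move some on-drug safety data into off-treatment summaries

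*SAP*

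**What the plan says.** SAP 6.6.4 applies whenever any part of the date is absent, be it day, month or year: "the last study drug dispensation date will be used as the end of treatment date for purposes of analysis". It does not separate a missing day from a missing month or year, and it makes no use of days supplied or capsules returned.

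Several definitions depend on last dose:
- **Adverse events (SAP 9.1).** An event with a complete onset date is treatment-emergent if it starts on or after first dose and "not more than 30 days after the date of the last dose of study drug". Later events are off-treatment events and are summarised separately.
- **Laboratory, vital sign and ECG data after early discontinuation (SAP 6.5.2.1).** Values count as on-treatment through 20 days after last dose.
- **Exposure (SAP 9.2).** Duration is last dose minus first dose plus 1.
- **Follow-up efficacy windows (SAP 6.5.2).** "All values included in the Week 103, 104, 108, and 112 analysis windows must also be assessed after last dose".

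Protocol 9.10.14 lists the dispensing visits. After Week 12 they are Weeks 24, 36 and 48, then "Week 52 (B), Week 64, Week 76, and Week 88". The quantity appears only as an example: "If the appropriate number of treatment kits (e.g., a 3-month supply) cannot be dispensed", a part supply may be given. Protocol 10.2 adds: "Each bottle of study drug will contain 30 capsules".

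**The concern.** Dispensation marks the start of a supply, and patients normally go on dosing after it. Using it as the end of treatment therefore usually places last dose too early. This is anti-conservative for safety, because events and measurements on drug are relabelled as off drug. The neighbouring SAP 6.6.3 leans the other way: it generally resolves incomplete adverse event dates towards treatment-emergent.

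The events most exposed include those that caused the patient to stop, since these occur near the true last dose. If that dose came more than 30 days after the last dispensation, such an event would drop out of the SAP 9.1.2 table of treatment-emergent events leading to permanent discontinuation and, where applicable, out of the serious and related tables. Likewise, an End of Treatment visit held 72 to 99 days after dispensation would be summarised under the 12-week off-treatment label in SAP Table 5.

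**Working it through.** The plan states no figure for this gap, so it is derived from the schedule.

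**Inputs.**
- Dispensing days: Day 1 and Weeks 2, 4, 6, 8, 12, 24, 36, 48, 52, 64, 76 and 88 (Protocol 9.10.14), with target days and windows from Protocol Table 4.
- Week 88 is Day 616 ±5. Week 100, the planned last dose, is Day 700, with up to 5 days early allowed and none late.
- Limits after last dose: 30 days for adverse events (SAP 9.1) and 20 days for laboratory, vital sign and ECG data (SAP 6.5.2.1).
- Bottle size: 30 capsules (Protocol 10.2).

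**Step 1: largest gap.** Gap = next dispensing day (or Week 100) minus dispensing day.

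| Interval | Scheduled gap | Gap with visit windows |
|---|---|---|
| Day 1 to Week 8 (4 intervals) | 13–14 days | 16–20 days |
| Weeks 8–12 and 48–52 (2 intervals) | 28 days | 34 days |
| Weeks 12–24, 24–36, 36–48, 52–64, 64–76, 76–88, 88–100 (7 intervals) | 84 days | 89–94 days |

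For the last interval, 700 − 616 = 84. Seven of the 13 intervals have the 12-week gap. Assuming three 30-day supplies, 3 × 30 = 90 days of drug are in hand. Gaps above about 90 days would then need missed doses.

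**Step 2: adverse events.** On-drug days relabelled = max(0, gap − 30).
- 84-day gap: 84 − 30 = 54 days (days 31 to 84), and 54/84 = 64%.
- With visit windows: 89 − 30 = 59 to 94 − 30 = 64 days.
- Gaps of 28 days or less: none. With visit windows, the 28-day intervals can reach 34 − 30 = 4 days.

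**Step 3: laboratory, vital sign and ECG data.** On-drug days relabelled = max(0, gap − 20). At 84 days this is 84 − 20 = 64 days (days 21 to 84), and 64/84 = 76%. At 28 days it is 8.

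**Step 4: exposure.** Duration runs to last dose, so it is short by the whole gap, up to 84 days.

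**Step 5: typical rather than maximum loss.** As an illustration, assume the true last dose is equally likely on each of days 0 to 84 after dispensation. The gap then exceeds 30 days in 54/85 = 64% of cases. The mean number of on-drug adverse event days relabelled is (1 + 2 + … + 54)/85 = 1485/85 = 17.5.

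**Step 6: primary endpoint.** For early discontinuers the follow-up windows run on study day, starting at Day 721 for Week 103 and Day 756 for Week 108. The latest scheduled dispensing day is 616 + 5 = 621. Supply from then ends at about 621 + 84 = 705 or 621 + 90 = 711, before Day 721. Values in these windows therefore follow last dose under either date. For completers, the SAP Table 4 footnotes fix last dose at the Week 100 dose.

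**The case against.** The strongest reply is that the rule will seldom matter.

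- **Few incomplete dates.** Completers take their last dose in clinic at Week 100. The protocol also requires a dosing diary, capsule counts and an End of Treatment visit close to last dose.
- **The full 84 days is an extreme.** A patient who finishes a 12-week supply normally reaches the next visit, where new drug resets the date or the Week 100 dose is witnessed.
- **Early signals are largely protected.** Protocol 5.1.2 places the fluid overload risk in the first three to four weeks, transaminase peaks two to four weeks after starting or increasing the dose, and most muscle spasms in the first two months. Scheduled dispensing gaps through Week 12 are at most 28 days.
- **Nothing is lost.** All adverse events, serious events and deaths are listed, and off-treatment events have their own summary.
- **SAP 9.2 has a matching convention.** If the final kit is not returned and no kit follows, it is assumed not taken.

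Most of this stands, and it limits the size of the point. It does not justify the rule. SAP 9.2 matches SAP 6.6.4 only for an unreturned final kit. When a used kit is returned, SAP 9.2 counts its doses as received in a period that the exposure calculation places after last dose. The in-clinic dose protects only patients who reach Week 100. SAP section 2 records that the decision to discontinue development went to all sites on 10 May 2023, so patients between visits may have taken their last dose away from the clinic.

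A reader might also infer that the off-treatment primary endpoint is contaminated. It is not, as Step 6 shows. Nor do all safety tables shift. Counts of patients crossing thresholds for transaminases, bilirubin, INR, alkaline phosphatase, ACR, magnesium, BNP, NT-proBNP and ECG parameters (SAP 9.5.2, 9.5.2.1 and 9.9) cover the whole study and do not use the last-dose date.

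**Conclusion.** The point holds as a limited defect in the safety conventions. Its direction is towards fewer treatment-emergent events. The maximum per patient, at scheduled visit timing, is 54 on-drug days for adverse events, 64 for laboratory, vital sign and ECG data, and 84 days of exposure. The tables exposed are the treatment-emergent event tables, the by-visit and on- versus off-treatment shift summaries, the on-treatment blood pressure categories in SAP 9.7, and exposure duration.

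This rests on two assumptions. The first is that the imputed end-of-treatment date is used as the date of last dose. The SAP does not say so, but a SAP Table 4 footnote treats the two as coinciding at Week 100, and no other rule covers a missing last-dose date. The second is that the patient went on dosing after the last dispensation.

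Two stronger readings are not supported. Dispensation is not strictly the earliest possible date, because the final kit may never have been started. The documents also give no basis for saying that patients with incomplete dates mostly stopped abruptly or were lost; an early stop within the interval would in fact shrink the error. The number affected is unknown and probably small.

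**What to change.** Replace the single rule in SAP 6.6.4 before database lock with the following:

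1. **Only the day is missing.** Use the last day of the recorded month, not earlier than the last dispensation date and capped at the earliest of drug return, last contact and death. Query any record whose month precedes the last dispensation.
2. **More is missing and the final kit was returned.** Use the dispensation date plus doses taken (dispensed minus returned), with the same caps and consistent with any known year.
3. **The final kit was not returned.** Adopt one convention and state it in both SAP 6.6.4 and SAP 9.2, so that exposure and doses received agree. For adverse event classification, add a sensitivity summary using dispensation date plus days supplied, with the same caps.

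The SAP should also say that this date is the last-dose date used in SAP 6.5.2.1, 9.1 and 9.2, and report by arm how many dates were imputed.

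The cost is a few lines of SAP text, a little programming on data already collected, one extra summary, and probably a slightly higher treatment-emergent event count.

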7. STUDY POPULATION

7.1. Subject Disposition

A disposition summary includes the number and percentage of patients in all analysis populations in the following categories:

- ITT population
- Safety population
- Received at least 1 dose at or after Week 52
- Completed treatment or follow-up through Week 52
 - Week 48 to Week 52 On-treatment
 - Week 48 to Week 52 Off-treatment
- Discontinued treatment prior to Week 100
 - Reason for discontinuing treatment
 - Treatment discontinuation related to COVID-19
- Completed study follow-up through Week 104
 - Completed treatment through Week 100
 - Discontinued treatment early but completed study visits
 - Discontinued treatment early but completed eGFR assessments through Week 104
- Completed study follow-up through Week 108
 - Completed treatment through Week 100
 - Discontinued treatment early but completed study visits
 - Discontinued treatment early but completed eGFR assessments through Week 108
- Completed study follow-up through Week 112
 - Completed treatment through Week 100
 - Discontinued treatment early but completed study visits
 - Discontinued treatment early but completed eGFR assessments through Week 112
- Completed study follow-up through Study Termination Date (STD)
 - Completed treatment through Week 100
 - Discontinued treatment early but completed study visits
 - Discontinued treatment early but completed eGFR assessments through STD
- Terminated from the trial before Week 112
 - Reason for study termination

- Study termination related to COVID-19
- Study week at study termination
- Terminated prior to STD
- Terminated after STD
- Number of patients by study visit
 - On treatment
 - Off treatment
 - In study follow-up
 - Stopped study

Patients who completed follow-up are defined as those who were in the study through Week 112 visit. A listing of disposition is provided for all enrolled patients.

7.2. Protocol Deviations

All protocol deviations are listed, and the frequency of patients with protocol deviations and major protocol deviations are summarized by deviation type and treatment group.

7.3. Demographic and Baseline Characteristics

Summaries of demographic and other baseline characteristic data are presented by treatment group for all analysis populations. They may also be summarized by randomized dose level (20 mg, 30 mg, or placebo).

The demographic and other baseline characteristics include:

- Baseline Age, Baseline Age category (<18, ≥18)
- Sex, Race, Ethnicity
- Weight (kg), Height (cm), BMI (kg/m²)
- Diastolic and systolic blood pressure (mmHg), Heart rate (bpm)
- Serum creatinine, eGFR, eGFR categorical status (<60, ≥60), eGFR Stratum
- ACR, ACR categorical status (≤300; >300), ACR Stratum
- KDIGO CKD progression risk score: color (Green, Yellow, Orange, Red) and cell in [Figure 2](#)
- CKD Stage ([Table 6](#))
- Angiotensin converting enzyme inhibitor (ACEi) treatment and/or Angiotensin II receptor blocker (ARB) (yes/no)
- Other baseline variables of interest

ADPKD related information includes:

- Age at ADPKD diagnosis
- Family history of ADPKD
- For patients with family history of ADPKD:
 - Sonography (indicating 3 or more cysts) for adult patients
 - Sonography (indicating 1 or more cyst) for adolescent patients
 - Computed tomography (CT) or magnetic resonance imaging (MRI) (indicating 5 or more cysts)
- For patients without family history of ADPKD:
 - Other cystic kidney diseases present
 - 10 or more cysts
- Use of Tolvaptan
 - Currently using Tolvaptan
 - Previously used Tolvaptan
 - Never received Tolvaptan
- [REDACTED]

7.4. Listing of Subject Inclusion and Exclusion Criteria

A listing of screened patients who did not meet inclusion or exclusion criteria is generated.

7.5. Medical History

Medical history is summarized by treatment. Medical history is coded using MedDRA (Medical Dictionary for Regulatory Activities). Medical history items are summarized by MedDRA system organ class (SOC) and preferred term (PT). A by-patient listing of medical history will be provided.

7.5.1. Historical eGFR

To characterize disease progression prior to trial entry, up to 5 years of historical serum creatinine values are collected for each patient as part of their medical history. Collection of historical serum creatinine is subject to availability of data from medical records; therefore, the number of available values will vary by patient and some patients may have no historical values. Historical serum creatinine values are converted to mg/dL and eGFR is calculated for analysis according to the appropriate equation (Section 6.5.4) using the patient age at laboratory collection for adult patients, or patient height at Screening for adolescent patients. Historical serum creatinine values were analyzed at various local laboratories (i.e., not collected as part of central lab data). Therefore, historical serum creatinine and corresponding eGFR values are considered part of a patient's medical history, and distinct from central lab assessments collected as part of the trial.

The eGFR values used in the analysis dataset for the baseline label (Table 8) are the baseline eGFR values for each patient (defined in Section 6.4.2), not the individual Screen A, Screen B, and Day 1 eGFR values.

Historical values are prior to first dose and have a negative Study Day value:

- $\text{Study Day} = (\text{Date of Historical Lab Collection}) - (\text{Date of Screen A})$

Summary statistics of eGFR results by historical year (listed in Table 8) will be presented for the ITT population. Summary statistics of available historical eGFR results are based on the following analysis windows:

Table 8: LABELS FOR SUMMARY OF HISTORICAL CHANGE IN eGFR

Analysis Visit	Label	Study Day Windows
-5	Historical Year 5	1825 to 1461 days prior to Screen A
-4	Historical Year 4	1460 to 1096 days prior to Screen A
-3	Historical Year 3	1095 to 731 days prior to Screen A
-2	Historical Year 2	730 to 366 days prior to Screen A
-1	Historical Year 1	365 to 1 days prior to Screen A
0	Baseline	Screen A to Day 1

The summary statistics will include the average eGFR value by patient and analysis time point. For instance, if multiple values are listed in the historical Year 1 results for a given patient, the average of those values is used to calculate the summary statistics.

